2. ANALYSIS SETS / TREATMENT GROUPS

2.1. Analysis sets

Full Analysis Set

The full analysis set (FAS) will consist of all subjects who have been randomized in the study. Subjects will be classified according to their assigned treatment arm.

Safety Analysis Set

The safety analysis set (SAS) is defined as the set of all subjects who have received at least one dose of S95014 in the study. Subjects will be classified according to treatment received. The safety endpoints will be analysed in the safety analysis set, unless otherwise specified.

Pharmacokinetic Analysis Set

The pharmacokinetic analysis set (PKAS) will include all subjects who have received at least one dose of IMP and are evaluable for PK analysis. The PK dataset will include only the subjects who had enough samples collected to provide interpretable PK results with no deviations that might have affected the PK interpretation (e.g. infusion interrupted for any reason, deviation in the theoretical administered dose > 10%, at least one missing PK sample during the 48 first hours, ≥ 2 missing PK samples after the 48-hour time point). The ADA-positive subjects will be a priori included in the PKAS since no impact was identified based on the population PK model. Nevertheless, if any evidence of such an impact can be identified in the study, a second PKAS will be defined that will include the subjects for whom none of the ADA assessment time points is positive.

Immunogenicity Analysis Set

The immunogenicity analysis set (IAS) will include all subjects who have received at least one dose of IMP and have at least one post-dose sample evaluable for immunogenicity testing.

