# 5.8. Participant withdrawal

#### 5.8.1. Withdrawal criteria

Information to be collected during the last visit of these participants is given in section 5.8.2. These follow-up modalities are used to ensure safety evaluation of all participants who received the IMP.

The reasons for premature discontinuation of the study are:

- Adverse events according to the judgement of the investigator, including no recovery of safety parameters, serious hypersensitivity or adverse events delaying the IMP administration by more than 14 days (see section 6.1.1)
- Pregnancy
- **Major deviation to protocol** if it interferes with the study evaluations and/or if it jeopardises participant's safety
- Non-medical reason (e.g. consent withdrawal, participant's removal)
- Other, physician decision

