#### 9.3. Assessment of immunogenicity

The occurrence of neutralizing antibodies and associated asparaginase inactivity can be related to a potential silent inactivation, which is characterized by the formation of neutralizing antibodies and reduced asparaginase activity in the absence of a clinically evident allergic reaction (Van der Sluis, 2016).

Immunogenicity assessment will include the detection of binding antibodies against S95014 as well as antibodies against PEG in samples taken during the treatment period, at pre-dose, 14 days and 25 days post dose (i.e. Day 17 and Day 28). The test item is the presence or absence of the production of anti-drug antibodies (ADA).

This evaluation will be based on qualitative enzyme-linked immunosorbent assays (ELISA) using S95014 as coating antigen. All positive samples will be further confirmed by competitive ELISA for the presence of binding anti S95014 antibodies. Samples, when confirmed positive, will then be assayed for anti-PEG antibodies. For all these assays, antibody status (positive or negative) will be reported.

The antibody positive samples will be further diluted and tested, and the highest sample dilution with a positive result will be reported as the anti-drug antibody titer.

In the absence of a validated neutralizing antibody assay, the neutralizing potential of antidrug antibodies in positive samples will be evaluated based on the concomitant results of the serum asparaginase activity.

All assays are validated with respect to cut-point, precision, linearity, short-term stability, freeze-thaw stability and drug interference.

Patients positive for ADA should be monitored every 3 months in the roll-over study protocol.

All samples will be destroyed after mandatory assessment is completed and at the latest before the final version of the clinical report.

The sampling conditions, labelling, handling and storing details will be described in a specific technical document.

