## **Immunogenicity Analysis Set**

The immunogenicity analysis set will include all subjects who have received at least one dose of IMP and have at least one post-dose sample evaluable for immunogenicity testing.

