3.8. Immunogenicity Analysis

The immunogenicity analysis will be performed on the Immunogenicity Analysis Set (IAS). The assessment of anti-drug antibodies includes binding and neutralizing antibodies to S95014 and binding anti-PEG antibodies.

The number and proportion of subjects in the immunogenicity analysis set having anti S95014 \pm anti-PEG antibodies at pre-dose, and 14 and 25 days (i.e. Day 17 and Day 28) after the administration of either liquid or lyophilized S95014 during the induction phase will be summarized by treatment group.

Results will be reported as follows:

- Pre-existing anti-S95014 or anti-PEG antibodies: number and proportion of samples confirmed positive at baseline.
- Seroconversion upon treatment: number and proportion of samples converted from negative at baseline to positive at Day 17 and Day 28. If a confirmed positive sample at baseline has titer increase at Day 17 or Day 28 by at least 4-fold (boosted ADA responses) then it will be included within the seroconverters. If a patient was negative at baseline, and ended up with a positive titer of "2" for example, post-treatment, this case was considered as a seroconversion despite the fact that the titer was not a 4 fold rise.

On a case-by-case approach, the impact of positive anti S95014 and anti-PEG antibodies will be investigated:

- On the pharmacokinetics through the temporal association of antibodies with the loss of asparaginase activity (neutralizing antibodies)
- On the safety through the temporal relationship with treatment-emergent hypersensitivity and anaphylactic reactions.

A patient with missing baseline will be considered as negative baseline to be conservative.

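### SAP 3.8 reports pre-dose antibodies only in patients with a post-dose antibody sample, so a dosed patient who leaves before Day 17 can be missing from the pre-existing antibody rate

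*SAP*

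**What the plan says.** SAP 2.1 and Protocol 10.1.2 define the IAS in the same way. In the protocol, "The immunogenicity analysis set will include all subjects who have received at least one dose of IMP", and both documents add that they must "have at least one post-dose sample evaluable for immunogenicity testing".

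SAP 3.8 opens by placing the immunogenicity analysis on this set. It then calls for "The number and proportion of subjects in the immunogenicity analysis set having anti S95014", with or without "anti-PEG antibodies at pre-dose, and 14 and 25 days (i.e. Day 17 and Day 28", by treatment group. The next item, pre-existing antibodies, is a count and proportion of baseline-positive samples, and no other analysis set is named for it.

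Protocol 10.2.5 is looser. It names no set, and its patient-level proportion covers only Day 17 and Day 28. The explicit tie between the pre-dose time point and the IAS therefore comes from the SAP.

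On timing, Protocol 9.3 places antibody testing "in samples taken during the treatment period, at pre-dose, 14 days and 25 days post dose (i.e. Day 17 and Day 28". The investigation schedule in Protocol 4.1.2 shows no antibody sample at the withdrawal/end-of-study visit, and the withdrawal procedure in Protocol 5.8.2 does not ask for one.

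On early exit, the adverse-event reasons for discontinuation in Protocol 5.8.1 are described as "including no recovery of safety parameters, serious hypersensitivity or adverse events delaying the IMP administration" beyond a set delay. Protocol 8.6.4 also says that patients with serious hypersensitivity reactions are to be discontinued from the study.

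On missing data, SAP 3.2, SAP 3.8, and Protocol 10.2.5 and 10.3 treat a missing baseline antibody result as negative.

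**The concern.** Antibody status before the first dose is a baseline characteristic. Under the SAP rule, whether a patient counts towards it depends on something that happens after dosing: staying long enough to give a Day 17 or Day 28 sample. That would be harmless if early exit had nothing to do with pre-dose antibodies. One exit route that the protocol foresees, serious hypersensitivity, may be related to them. SAP 3.8 itself plans to look at that link: "On the safety through the temporal relationship with treatment-emergent hypersensitivity and anaphylactic reactions".

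For such a patient the pre-dose sample is the only scheduled antibody result, and the pre-existing rate would leave it out. The rate is too low if early leavers are positive more often than the arm as a whole, and slightly too high if they are positive less often. What is at stake is the accuracy of one descriptive row, by arm, under the secondary immunogenicity objective.

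**Working it through.** **Plan's own figure.** There is none to reproduce. Neither document states an expected antibody rate, reaction rate or number of early leavers.

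**Step 1: who is counted.** Take a patient who is dosed on Day 3, has the pre-dose sample, and leaves before Day 17.
- Safety Analysis Set (SAP 2.1: at least one dose): in.
- IAS (SAP 2.1: at least one dose and an evaluable post-dose antibody sample): out, unless an unscheduled sample was taken, because no antibody sample is scheduled between pre-dose and Day 17 or at withdrawal.
- Pre-dose summary in SAP 3.8 (IAS): out, although the pre-dose sample is scheduled.

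**Step 2: formula.** Let n be the dosed patients in one arm, all with a pre-dose result; a the number positive at pre-dose; r the number lost before Day 17 with no post-dose antibody sample; and k the number positive among those r.
- Rate in all dosed patients: a/n.
- Rate reported under the SAP: (a − k)/(n − r).

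The reported rate is lower than a/n when k/r is greater than a/n, and higher when k/r is smaller. The two are equal if r = 0, if a = 0, or if the lost patients have the same positive rate as the arm.

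**Step 3: inputs.** n = 88/2 = 44, taking the 88 patients to be included (SAP 1.3) as all dosed and split evenly. This is an assumption. The values of a, r and k are also assumed, with r = 1 or 2.

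**Step 4: results for a = 4 (4/44 = 9.1%).**

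| r | k | Reported rate | Change (percentage points) |
|---|---|---|---|
| 1 | 0 | 4/43 = 9.3% | +0.2 |
| 1 | 1 | 3/43 = 7.0% | −2.1 |
| 2 | 0 | 4/42 = 9.5% | +0.4 |
| 2 | 1 | 3/42 = 7.1% | −1.9 |
| 2 | 2 | 2/42 = 4.8% | −4.3 |

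The 95% Clopper-Pearson interval for 4/44 is 2.5% to 21.7%, so every reported value lies inside the sampling uncertainty of the true one.

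**Step 5: other assumed values of a, with r = 1 or 2.**
- a = 0: 0% either way, no effect.
- a = 1 (1/44 = 2.3%): reported as 0.0% to 1/42 = 2.4%.
- a = 2 (2/44 = 4.5%): reported as 0/42 = 0.0% to 2/42 = 4.8%.
- a = 8 (8/44 = 18.2%): reported as 6/42 = 14.3% to 8/42 = 19.0%.

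With few positives, the lower end means that pre-existing antibodies could be reported as absent in an arm where one or two patients had them.

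**The case against.** The strongest reply is that this is small and partly a matter of preference. The result is descriptive, with no test or decision rule. The largest drop for 4/44 needs both lost patients to be positive, which is half of all positives in the arm. Patients are newly diagnosed and untreated, and a history of PEG sensitivity is an exclusion criterion (Protocol 4.1.1 and 5.2.2), so there may be few or no baseline positives. Loss before Day 17 is possible but not stated: the protocol discontinues patients with serious hypersensitivity without saying when their antibody sampling stops, and it sets the end-of-study visit at least 30 days after infusion. A single set for pre-dose, Day 17 and Day 28 also lets the rows be read against one denominator. Finally, SAP 3.3 and 3.3.1 already tabulate membership of each analysis set by arm, so the gap between the safety set and the IAS will be visible.

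All of this stands, and it limits the weight of the point. It does not remove it. The disposition table shows how many dosed patients fall outside the IAS, but not their pre-dose antibody status.

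The pre-existing item counts samples rather than patients, so its denominator is less explicit than that of the patient-level proportion. One pre-dose sample is scheduled per patient, however, and the section's opening sentence ties the item to the IAS.

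A reader might also infer that the case-by-case review of antibodies against hypersensitivity omits early leavers. The documents do not show that. It is an individual review with no stated population, and the listing templates are in a separate document (SAP 1). Nor can the 10% allowance for patients not evaluable for PK be read as a forecast of early exits: a missed early PK sample is enough to make a patient non-evaluable (Protocol 7.1), and that patient can still give Day 17 and Day 28 antibody samples.

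**Conclusion.** The point holds as a limited one. On the text, the pre-existing antibody rate is restricted to patients with an evaluable post-dose sample, so a dosed patient who leaves before Day 17 without an unscheduled sample is not counted. This follows from the set definition and the sampling schedule and needs no assumption.

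The size does rest on assumptions: 44 dosed per arm, every pre-dose sample evaluable, 4 positive, and 1 or 2 early losses. Under these, 9.1% is reported as 4.8% to 9.5%. The direction depends on whether the lost patients are positive more or less often than the arm, which the documents do not tell us. There is no effect if nobody leaves early or if nobody is positive at baseline.

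A reader might go further and infer a material bias in the trial's conclusions. The documents do not support that. The primary PK comparison uses a different set, reactions are reported in the Safety Analysis Set (SAP 2.1 and 3.6.1), and the Day 17, Day 28 and seroconversion results properly need a post-dose sample. This is an optional improvement to one secondary table.

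**What to change.** In SAP 3.8:

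1. Report pre-existing anti-S95014 and anti-PEG antibodies by arm in Safety Analysis Set patients with a measured pre-dose antibody result.
2. Keep the IAS for the Day 17, Day 28 and seroconversion results.
3. State that the rule imputing a missing baseline as negative (SAP 3.2 and 3.8) applies only to the seroconversion classification and not to the pre-existing rate. Otherwise a patient with no pre-dose result would be counted as a measured negative. Under this wording that patient is outside the baseline row but remains baseline-negative for seroconversion.
4. Footnote the two denominators in the table.

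The cost is SAP wording, a second denominator and a footnote in one table. It uses samples already scheduled and needs no new data. The downside is that the baseline and seroconversion rows no longer share a denominator, which the footnote must make plain. No change is proposed to any discontinuation rule or to the case-by-case hypersensitivity review.

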2.2. Treatment groups

S95014 liquid (reference drug) and S95014 lyophilizate (test drug) are both IMPs.

- Arm 1: lyophilized S95014 reconstituted will provide 5 mL of extractable volume with the concentration of 750 U/mL. The vial of lyophilized powder (3.750 U/vial) is reconstituted with 5.2 mL of SWFI to obtain a 750 U/mL solution for single use.
- Arm 2: liquid S95014 is provided as 3.750 U per 5 mL solution in a single use vial to obtain a 750 U/mL solution for single use.

S95014 (either liquid or lyophilized) will be intravenously administered over 1 hour at the dose of 2500 U/m² at Day 3 of the induction phase. Subjects will receive other backbone chemotherapy agents as per ALL-MB 2015 protocol.

3. STATISTICAL METHODS

3.1. General considerations

All data processing, summarization, and analyses will utilize SAS® software package, Version 9.3, unless otherwise specified.

3.1.1. Descriptive statistics

For **qualitative data**, number of observed values, number and percentage of subjects per class will be presented. Unless otherwise specified in the TLG, no class "Missing" is considered.

For **quantitative data**, number of observed values, mean, standard deviation, median, first and third quartiles, minimum and maximum will be presented. For lognormal-distributed PK parameters, coefficient of variation (CoV), geometric mean and geometric CoV will also be presented.

3.1.2. General definitions

Unless specified otherwise in section 3.3 to 3.5, the following definitions will be considered:

- Analysable value will be defined as any non-missing value.
- Baseline value will be defined as the last analysable value prior to the first IMP intake (i.e. before or the same date as the first IMP intake date).
- Post-baseline value will be defined as any value recorded at a given timepoint after baseline.
- Change from baseline will be defined as the arithmetic difference between a post-baseline value and the baseline value for a given variable at a given time point.

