# 5.4.2. Medical and therapeutic criteria

- 24. Inadequate hepatic function (total bilirubin > 1.5 times upper limit of normal (ULN), transaminases > 5 x ULN)
- 25. Inadequate renal function defined as serum creatinine > 1.5 x ULN

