#### Laboratory tests

All laboratory tests performed during the study period will be assayed in an identified laboratory at hospital. Inter-visits laboratory tests could be assayed by local laboratories. In all cases, the full validated set of normal ranges values will be collected, as well as any update in these values during the study and must be documented in the corresponding eCRF pages.

All samples will be destroyed after mandatory assessment is completed and at the latest before the final version of the clinical report.

The laboratory parameters collection plan is described in Table (8.2) 1.

Blood haematology, blood biochemistry, blood coagulation and urinary analysis will be performed during screening, before S95014 infusion (Day 3, pre-dose), at Day 10, Day 17, Day 24 and during the withdrawal/end-of-study visit.

Other laboratory tests (i.e. hepatitis serology and pregnancy test) will be performed during screening and during the withdrawal/end-of-study visit.

**Test Category** Test Name Haematology Haematocrit, Haemoglobin, Red blood cells (RBC), White blood cells (WBC), Platelets, Differential (Basophils, Eosinophils, Lymphocytes, Monocytes, Neutrophils, Blasts in absolute value and in %) Albumin, Alkaline Phosphatase (ALP), ALT, AST, Ammonia, Bicarbonates, Gamma-Biochemistry glutamyl-transferase (GGT), Lactate dehydrogenase (LDH), Calcium, Phosphorus, Sodium, Potassium, Creatinine, Total Bilirubin, Total Cholesterol, LDL, HDL, Triglycerides, BUN or Urea, Uric Acid Amylase, Lipase, Glucose Urinary analysis Macroscopic Panel (Dipstick) (Blood, Glucose, Ketones, Protein) If the dipstick test is at least 2+ on one or more parameter(s), quantitative urinary biochemistry tests will be performed on the abnormal parameter(s) Prothrombin time - International Normalized Ratio (INR), fibrinogen, protein S activity, Blood coagulation antithrombin activity, activated Partial Thromboplastin Time (aPTT), D-dimer, FDP HbsAg, HbsAb, HbcAb, if HbsAg or HbcAb positive check viral load (HBV-DNA) at Hepatitis serology baseline, HCV RNA-PCR, HEV RNA-PCR Pregnancy Test Pregnancy testing is mandatory at inclusion (serum) and at withdrawal/end-of-study visit (serum) for WOCBP

Table (8.2) 1 - Local Clinical laboratory parameters collection plan

All samplings for biochemistry should be taken in fasting conditions.

Abnormal laboratory values or test/exams results (i.e. ECG recording) will constitute an AE if they are:

- associated with signs and symptoms, or

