1.2.1. Study plan

Each patient will be randomly assigned (1:1) to either lyophilized (arm 1) or liquid (arm 2) S95014 intravenously at the dose of 2500 U/m² at Day 3, in combination with other backbone chemotherapy agents as per local practice.

The study duration will be approximately 1.5 month, including the screening (14 days) and the treatment period consisting of the induction phase (approximately 30 days). After completing the induction phase, patient will be discontinued from the study and, provided that the inclusion/non-inclusion criteria are fulfilled, will be proposed to enter into a roll-over study (CL2-95014-003) for the consolidation phase.

[figure not shown]
The study will be divided into the following periods for each participant:

- **Screening visit (up to 14 days prior to inclusion):** to obtain informed consent and check the screening/non-screening criteria.
- **Screening period (Day -14 to Day -1):** to check the eligibility of the patient to be included in the study within 14 days prior to the inclusion.
- **Inclusion visit (Day 0):** to check inclusion/non-inclusion criteria and to confirm inclusion of the patient in the study

- **Randomization (Day 0):** the day of inclusion visit (i.e. Day 0), included subjects will be randomly assigned to one of the two treatment groups:
 - Lyophilized S95014 (arm 1)
 - Liquid S95014 (arm 2)
- **Infusion (Day 3):** the day of S95014 infusion, based on randomized treatment group.
- **Treatment period:** treatment period will start from the day of S95014 infusion, corresponding to Day 3 of the induction phase, until the withdrawal/end-of-study visit.
- **Withdrawal/End-of-study visit:** at least 30 days after S95014 infusion (i.e. Day 33) and before starting the consolidation phase. During the withdrawal/end-of-study visit, subjects will be proposed to participate in a roll-over study (CL2-95014-003) for the consolidation phase using lyophilized S95014 in combination with backbone regimen as per ALL-MB 2015 protocol.

The study plan is shown in Figure (1.2.1) 1.

Figure (1.2.1) 1 - Study plan

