3.6.2. Other Safety Evaluations

Descriptive statistics of laboratory parameters and continuous variables of vital signs will be calculated by treatment group for each time point. Shift tables for qualitative urinalysis results at each time point after the start of administration will be created. Height, weight, body surface area (BSA) and body mass index (BMI) will be summarized over visit by treatment group.

Shift tables will be provided for laboratory parameters to compare a subject's baseline laboratory evaluation relative to the worst value during the treatment period using Common Terminology Criteria for Adverse Events (CTCAE) v5.0 grades. In addition, the normal laboratory ranges will be used to evaluate whether a particular laboratory test value was normal, low, or high for each visit value relative to whether or not the baseline value was normal, low, or high. Subjects with abnormal laboratory values will be listed and values outside the normal ranges will be flagged.

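### Is the Day 3 pre-dose laboratory sample both the baseline and a candidate worst value in the graded shift tables?

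*SAP*

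**What the plan says.** Four places in the SAP and one in the protocol bear on this.

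- **Baseline.** SAP 3.1.2 takes "the last analysable value prior to the first IMP intake (i.e. before or the same date as the first IMP intake date"). Its scope statement reads "Unless specified otherwise in section 3.3 to 3.5, the following definitions will be considered", so the definition carries into the safety analyses of 3.6. The same list adds: "Post-baseline value will be defined as any value recorded at a given timepoint after baseline".
- **Treatment period.** SAP 1.2.1, in its outline of study periods, says the "treatment period will start from the day of S95014 infusion, corresponding to Day 3 of the induction phase", and runs it to the withdrawal/end-of-study visit. Protocol 4.1.1 says the same.
- **Shift tables.** SAP 3.6.2 compares a subject's "baseline laboratory evaluation relative to the worst value during the treatment period" by CTCAE grade. Just before this, the section asks for shift tables of "qualitative urinalysis results at each time point after the start of administration".
- **Adverse event window.** SAP 3.6.1 counts an event as treatment-emergent from the infusion itself, labelled Day 3, to the same end point.
- **Laboratory schedule.** Protocol 8.2 places haematology, biochemistry, coagulation and urinalysis at screening, then "before S95014 infusion (Day 3, pre-dose), at Day 10, Day 17, Day 24 and during the withdrawal/end-of-study visit".

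**The concern.** The baseline window closes on the infusion date and the treatment period opens on it. The Day 3 pre-dose sample therefore falls into both if dates alone are compared. SAP 3.6.2 does not use the term post-baseline for the graded table, although 3.1.2 defines it, and it does not repeat the restriction it places on urinalysis.

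On that reading a baseline value is compared with a maximum that includes itself. No patient could move to a better grade. An abnormality present before the infusion that later resolves would be shown as an abnormality of that grade during treatment. A patient with a Day 3 sample and no later laboratory value would appear as unchanged instead of missing. Two programmers working from the same text could produce different tables.

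**Working it through.** The plan states no figure on this point, so there is none to reproduce. The check maps samples to windows and then compares the two readings.

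**1. Samples in each window** (schedule from Protocol 8.2).

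- Eligible as baseline: screening and Day 3 pre-dose. The later one is used, so Day 3 pre-dose.
- In the treatment period by calendar day: Day 3 pre-dose, Day 10, Day 17, Day 24, end of study = 5.
- After the infusion: Day 10, Day 17, Day 24, end of study = 4.
- Overlap: 5 − 4 = 1 scheduled sample. If Day 3 is missing, screening becomes baseline and the overlap disappears for that patient.

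The only scheduled laboratory sample on Day 3 is pre-dose. The same-date allowance in SAP 3.1.2 therefore selects the right laboratory baseline whether dates or clock times are used.

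**2. Effect on the graded table.** Let b be the baseline grade and p the worst grade after the infusion, each 0 to 4, giving 5 × 5 = 25 combinations. By calendar day the worst value is max(b, p); with post-baseline values only it is p.

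| Result | Calendar-day reading | Post-baseline only |
|---|---|---|
| Worse than baseline | 4+3+2+1+0 = 10 | 4+3+2+1+0 = 10 |
| Unchanged | 25 − 10 − 0 = 15 | 5 |
| Better than baseline | 0 | 0+1+2+3+4 = 10 |

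Worsening agrees in every combination, because max(b, p) > b exactly when p > b. The calendar-day reading only moves 10 combinations from better to unchanged. For example, grades 3, 2, 1, 0, 0 across the five samples give 3 to 3 by calendar day and 3 to 2 with post-baseline values only. These are counts of possible patterns, not patient rates.

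**3. Which reading the SAP supports.** The calendar-day boundary comes from a description of study periods in 1.2.1, not from the analysis definitions in 3.1.2. Where the SAP sets a window for a safety analysis, in 3.6.1, it starts at the infusion. The definitions in 3.1.2 treat baseline and post-baseline as separate values, and a table that sets one relative to the other presupposes two different measurements. The urinalysis sentence points the same way.

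**4. Other outputs.** The normal/low/high comparison in 3.6.2 is made visit by visit, so at most it gains a trivial Day 3 against Day 3 row. Treatment-emergent and special-interest events use the 3.6.1 window. The primary analysis uses plasma asparaginase activity and does not draw on these tables.

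**The case for a change.** The best case for an edit is that the SAP should not depend on a programmer's convention. Its authors defined post-baseline and did not use it here; they restricted the urinalysis tables and not these. Abnormal Day 3 values are plausible. Patients have newly diagnosed leukaemia, eligibility sets no numeric limit on blood counts or coagulation values, and the hepatic criterion excludes only "transaminases > 5 x ULN" among transaminase results. Eligibility is checked at Day 0, and Protocol 6.1.1 lets the infusion be delayed by up to 14 days, so Day 3 values are not strictly held to those limits. Changing a phrase would cost almost nothing.

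Part of this stands. The literal overlap is real, and abnormal Day 3 blood counts are to be expected. A patient without follow-up would be shown as unchanged on the calendar-day reading and would enter the denominator.

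The rest is weaker. Protocol 8.6.1 puts Grade 3 AST or ALT above 5.0 × ULN, so the transaminase criterion already excludes Grade 3 at inclusion. Protocol 5.2.2 also excludes known coagulopathy and laboratory abnormalities that the investigator considers significant. A shift from 3 to 3 displays its own baseline grade, so a resolved abnormality is not presented as new. Improvement remains visible in the by-visit comparisons, the descriptive statistics at each time point and the flagged listings. The table templates, which SAP section 1 places in a separate document, are the natural home for such a filter.

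The same-date wording in 3.1.2 is also imprecise for vital signs, which are taken before and after the infusion on Day 3. Its main clause still requires a value prior to the infusion, and SAP 3.6.2 names no change-from-baseline analysis of vital signs.

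**Conclusion.** No change to the plan is needed. This is a gap in wording that analysts fill sensibly: the ordinary reading compares the Day 3 pre-dose baseline with the 4 later scheduled values and any unscheduled later ones.

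Even on the calendar-day reading, the effect is confined to one set of descriptive tables. Ten of 25 cells would stay empty, the number of patients who worsen would not change, and no conclusion about PK comparability or adverse events would move. Cells differ only for patients whose later values are all of lower grade than Day 3, or who have no later value. The documents give no basis for counting them.

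This rests on two assumptions: that the tables use grades 0 to 4, and that the separate templates, which are not available here, do not impose the calendar-day reading. If the SAP is revised for other reasons, its authors could use the post-baseline term from 3.1.2 in 3.6.2, but nothing in the trial depends on it.
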